Test whether theta-burst stimulation to the frontal eye fields (FEF) alters short term memory relative to sham stimulation.	Increases or decreases in accuracy and trial-to-trial variability in the memory-guided saccade task.	Criticality affords greater dynamic susceptibility to afferent inputs. As such, brains operating closer to criticality will more dynamic instability, undermining performance on tasks dependent on short term memory stability. Theta-burst manipulations which push brains closer to criticality will thus produce greater trial-to-trial variability in accuracy and reaction times on tasks	A decrease in the E/I balance in the FEF following cTBS or an increase in E/I balance following iTBS will make the FEF operate closer to criticality for some people and farther away for others. Operating closer to criticality as a consequence of TMS will thereby cause instability in the short-term

OBJECTIVES	ENDPOINTS	JUSTIFICATION FOR ENDPOINTS	PUTATIVE MECHANISMS OF ACTION
		including memory-guided saccades.	memory representations needed for memory-guided saccades.
Test whether cTBS increases and iTBS decreases subjective cognitive effort associated with task switching between anti- and pro-saccades.	Task switch costs and effort discounting of rewards contingent on the expenditure of cognitive effort following active versus sham FEF stimulation.	Task switching is effortful and subjectively costly, producing effort avoidance. Brains operating closer to criticality have more dynamical flexibility and so should reduce switch costs and subjective effort.	A decrease in the E/I balance in the FEF following cTBS or an increase in E/I balance following iTBS will make the FEF operate closer to criticality for some people and farther away for others. Operating closer to criticality as a consequence of TMS will thereby cause result more dynamical flexibility reducing the energy required to shift neural dynamics between tasks, and thereby produce lower effort costs.
Secondary			
Tertiary/Exploratory			

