## 6 STUDY INTERVENTION(S) OR EXPERIMENTAL MANIPULATION(S)

### 6.1 STUDY INTERVENTION(S) OR EXPERIMENTAL MANIPULATION(S) ADMINISTRATION

#### 6.1.1 STUDY INTERVENTION OR EXPERIMENTAL MANIPULATION DESCRIPTION

The study intervention is modulation of cortical excitation to inhibition (E/I) balance in the right frontal eye field (FEF) by means of 2 trains of spaced continuous theta burst stimulation (cTBS) or intermittent theta burst stimulation (iTBS) using a transcranial magnetic stimulation device. As prior work (Huang et al 2005; Chung et al. 2018) has shown that cTBS reliably decreases the cortical E/I ratio with diverse cortical targets and iTBS increases the E/I ratio, we expect to replicate a reduction in E/I balance when cTBS is applied to the FEF and an increase in E/I balance when iTBS is applied. The mechanism of action is thought to be a manipulation of inhibitory neurotransmission across diverse timescales. The endpoint of this stimulation will be a modulation of the local E/I ratio that should last at least 60 minutes post-stimulation (Chung et al., 2016).

We will assess the changes in E/I balance by quantifying the functional E/I ratio as previously done in a study of the GABA receptor agonist Zolpidem (Bruining et al. 2020). We furthermore anticipate that a reduction in FEF E/I balance will also make the dynamics of FEF more sub-critical while an increase would make FEF more super-critical (Pfeffer et al. 2018; Poil et al. 2012). Thus, depending on whether participants' brains operate in a sub- or super-critical regime at baseline, we predict that cTBS and iTBS manipulations will either make their brains operate closer to or farther from criticality. If cTBS / iTBS make participants' brains operate closer to criticality, this will be reflected by an inferred functional E/I ratio of 1.0, and stronger long range temporal correlations. Conversely values farther from 1.0 will correspond with weaker long-range temporal correlations otherwise found in the brain in a critical state. Moreover, we will test the prediction that cTBS / iTBS to the FEF will affect oculomotor control. Specifically, we predict that since criticality affords maximal susceptibility and flexibility, tasks which require more stability (e.g. short term memory tasks) will be performed with less precision and more trial-to-trial variability in accuracy and reaction times at criticality. Since criticality also maximizes information transfer capacity,

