performance will increase for tasks which require better inter-regional communication (e.g. top-down control tasks) when brains operate near criticality. Hence we specifically predict that TMS manipulations which make the FEF operate closer to criticality will result in worse and more variable memory-guided saccade task performance, and better and more consistent anti-saccade task performance.

Importantly, we will contrast the effects of active cTBS and iTBS with sham stimulation. The double blind procedure involves flipping over the coil so that the participants' experience is as close as possible across active and sham conditions, and the experimenter will have no way of knowing which is which (both sides of the coil are identical and flipped based on an internal blinding code within the stimulator unit) until experimental de-blinding.

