### 9.1 STATISTICAL HYPOTHESES

- Primary Endpoint(s):

We predict that, relative to pre-stimulation rest, continuous theta burst stimulation (cTBS) will result in a reduction of the local balance of cortical excitation to inhibition as reflected in the functional E/I balance in proximity to stimulated targets. Conversely, we predict that intermittent theta burst stimulation (iTBS) will result in an increase of the local balance of cortical excitation to inhibition as reflected in the functional E/I balance in proximity to stimulated targets. We also predict these changes to exceed any effects of sham stimulation, and thus another set of endpoints will compare the functional E/I balance after sham versus either active stimulation protocol.

We also predict that, relative to pre-stimulation rest, cTBS and iTBS protocols that will either reduce or strengthen markers of critical dynamics (including, e.g., long-range temporal correlations) in proximity to stimulation targets. The direction of the effect will depend on how the brain operates at baseline. For example a brain that operates in a more sub-critical (lower E/I balance) regime will show an increase in long-range temporal correlations following iTBS (because it should raise the functional E/I balance).

We also predict that, relative to sham stimulation, cTBS and iTBS will alter oculomotor task performance. Specifically, because criticality makes brains more flexible and susceptible, protocols which make brains operate closer to criticality will cause performance to become more variable and worse on the memory-guided saccade task which depends on stability of short-term memory representations. Also, because criticality increases information transfer capacity between brain regions, protocols which make brains operate closer to criticality will cause performance to become better on the anti-saccade task which depends on robust top-down communication of control signals to override bottom-up reflexive saccades to the target.

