We also predict that, relative to sham stimulation, cTBS and iTBS will alter subjective effort. We hypothesize that subjective effort reflects divergence from criticality associated with performing difficult tasks. Indeed, typically, brains become more sub-critical, on average, when performing demanding tasks. To measure subjective effort, we will examine cognitive effort discounting – a measure of the amount by which participants discount the offer to perform a more demanding version of tasks (in this case with frequent task switching between anti- and pro-saccades) versus a less demanding version of the task (in this case with minimal task switching between anti- and pro-saccades) for money. The amount of money people forgo to avoid the harder task quantifies the subjective effort cost they experience. We predict

that people whose brains diverge more from criticality during task performance will show steeper effort discounting, and that cTBS or iTBS protocols that minimize divergence from criticality during the task will show shallower effort discounting.

We also hypothesize that subjective effort reflects divergence from a critical state and that criticality depends on the E/I balance. As such, we predict that there will be individual difference correlations in the degree to which TMS perturbs E/I balance, alters measures of criticality including long-range temporal correlations, and ultimately amplifies subjective effort.

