## 9.4 STATISTICAL ANALYSES

### 9.4.1 GENERAL APPROACH

There are no categorical outcomes. Key measures are all continuous outcomes, and are described in detail in the next section. They will be analyzed according to pre- versus post-stimulation means and also in sham versus active stimulation. We will also report standard errors for each outcome. Key outcomes have multiple associated measures. Multiple measures will be used to assess reliability by parallel forms.

We will use standard frequentist cut-offs of  $p < 0.05$  for all statistical tests, correcting for multiple comparisons. Key t-tests will include pre-post and sham-versus-active distinctions in E/I balance measures, oculomotor control task performance measures, and measures of criticality.

Covariates of no interest to be included are sex and age which we will incorporate via multiple regression to ask whether rTMS alters key outcomes (described in the next session).

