### 9.4.2 ANALYSIS OF THE PRIMARY ENDPOINT(S)

The following key outcomes will be assessed in this study. All measures are interval with the exception of the categorical covariate of sex.

- Subjective effort
  - Likert scale ratings (ranging from 1-10) of task-induced effort, demand, time pressure, and stress
  - subjective values as estimated from an indifference point discounting procedure
  - self-reported motivation to engage in demanding tasks on a set of Likert scales with continuous values ranging from 0-20
  - Pupil dilation as a continuous variable which has been shown to index the cognitive and physical effort associated with oculomotor tasks (Koevoet et al., 2024)
- E/I balance
  - fEI derived measure with exponents ranging approximately from 0.0-2.0
  - avalanche branching statistics with values approximately from 0.5 to 1.5
  - power-law exponents with exponents approximating -2.0
- Critical dynamics
  - Long range temporal correlations – a derived measure with exponents ranging approximately from 0.5-1.0
  - Avalanche size and duration distribution exponents approximating -2.0 and -1.5, respectively.

- Band-limited bistability with values ranging from 0.0 to ~5.0
- Memory guided saccade task performance
  - overall accuracy as degrees of visual angle
  - median reaction times in terms of time from cue until a saccade is launched
  - trial-wise variability in accuracy (SD)
  - trial-wise variability in reaction time (SD)
- Anti-saccade task performance
  - Overall accuracy rate as a percent of trials with correct anti-saccade versus incorrect pro-saccade
  - Median reaction times in terms of time from cue until a saccade is launched
  - trial-wise variability in accuracy (SD)
  - trial-wise variability in reaction time (SD)

Primary analyses of these outcomes will entail multiple regression models in which outcomes will be regressed on cTBS condition (target versus sham), controlling for sex and age.

We will also test for inter-correlations among the primary endpoint measures. Namely, these correlations will test whether the degree to which rTMS alters one measure (e.g. functional E/I balance) correlates with stimulation effects on other measures (e.g. endpoint variability on the memory-guided saccade task).

We will use Pearson's correlations for all tests since our outcome measures are continuous, interval measures.

---

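### The plan predicts that baseline regime sets the direction of change in long-range temporal correlations, but no planned analysis contains a baseline-by-condition term

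*Protocol*

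**What the plan says.** **The hypothesis.** Section 9.1, under the primary endpoints, predicts that either protocol may weaken or strengthen markers of criticality: "The direction of the effect will depend on how the brain operates at baseline". Its example is a sub-critical brain, whose long-range temporal correlations should rise after iTBS. Section 6.1.1 makes the same prediction, with the starting state as the deciding condition: "brains operate in a sub- or super-critical regime at baseline, we predict that cTBS and iTBS manipulations will either make their brains operate closer". The sentence there names movement away from the critical point as the alternative. In Section 3, the mechanism cells of the memory and effort rows say that stimulation "will make the FEF operate closer to criticality for some people and farther away for others".

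**Task outcomes.** Their predictions are stated in terms of moving closer to criticality. For anti-saccades, Section 9.1 says "protocols which make brains operate closer to criticality will cause performance to become better on the anti-saccade task", and Section 6.1.1 expects "better and more consistent anti-saccade task performance". For effort, Section 9.1 says "cTBS or iTBS protocols that minimize divergence from criticality during the task will show shallower effort discounting".

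**The analyses.**
- Section 9.4.1: "Key t-tests will include pre-post and sham-versus-active distinctions in E/I balance measures, oculomotor control task performance measures, and measures of criticality".
- Section 9.4.2: "outcomes will be regressed on cTBS condition (target versus sham), controlling for sex and age" (I read this as meant for both protocols), plus Pearson correlations between stimulation effects on different measures.
- Section 4.1 adds session order as a covariate.
- Section 9.4.7 (subgroups) is N/A. The only moderator in Section 9.4.9 is where and how strongly stimulation was delivered.
- Section 9 says there will be no formal SAP.

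**The concern.** If the sign of an effect differs between participants according to where they start, a mean contrast estimates the net result for this sample's mix of starting points. It does not address the claim that the starting point decides the sign. That claim is stated as a primary hypothesis and would go unanswered. A small average change in long-range temporal correlations could mean that stimulation did nothing, or that it moved participants in opposite directions. A clear average change would describe this sample's mix and might not carry over to another.

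The usual allowance that a SAP will supply the missing model does not apply, because the protocol says there will be none.

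Section 3 adds a second difficulty. Its first row predicts dampened long-range temporal correlations under both protocols. Its anti-saccade row and effort objective give cTBS and iTBS fixed, opposite directions. Sections 6.1.1 and 9.1 make direction depend on the participant. With both on paper and no prespecified test of the dependence, a result of either sign could be presented as predicted.

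**Working it through.** **1. The plan's own power figures.** Section 9.2 gives n = 60, p < 0.05, g = -1.14 (cTBS), 0.84 (iTBS) and a late iTBS effect of size 0.21 with 36% power. A two-sided paired t-test with noncentrality |g| x sqrt(60) gives 36.0% for 0.21 and more than 99.9% for 0.84 and 1.14. The one-sided test gives 48.5%, and independent groups of 60 give 20.7%. The stated figures therefore reproduce, as power for a mean within-person effect with one direction.

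**2. Hypothesis against analysis.**

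| Planned analysis | Can it test whether baseline sets direction? |
|---|---|
| Pre-post and active-sham t-tests | No, means only |
| Regression on condition, sex, age, session order | No baseline or interaction term |
| Correlation of change in one measure with change in another | No. It can show that a change in criticality goes with a change in performance |
| Subgroups | N/A |

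Correlations using signed functional E/I change have a further weakness. Section 9.1 fixes the sign of that change for each protocol, while the sign of the linked change in long-range temporal correlations flips with baseline. The within-regime slopes are opposite and dilute each other when pooled.

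**3. Loss in the average test, equal and opposite effects.** The regime mix p and this response model are assumptions. A share p responds +d and the rest -d, with noise SD 1. The mean is (2p - 1)d and the SD is sqrt(1 + 4p(1 - p)d^2). For d = 0.84 and p = 0.7 the mean is 0.4 x 0.84 = 0.336, the SD is sqrt(1 + 0.84 x 0.7056) = 1.262, and the standardised effect is 0.266. Simulated power, n = 60, two-sided 0.05:

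| d | 50:50 | 60:40 | 70:30 | 80:20 | 90:10 |
|---|---|---|---|---|---|
| 0.5 | 5% | 10% | 28% | 57% | 83% |
| 0.84 | 5% | 17% | 53% | 88% | 99% |
| 1.14 | 5% | 21% | 67% | 96% | 100% |

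The values 0.84 and 1.14 are motor-evoked-potential effects, borrowed only for scale.

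**4. The same question in a peaked model.** All inputs are assumptions. The marker is highest at E/I = 1, baseline E/I is N(m, 0.2) and the shift is N(s, 0.1). Active change is -(post - 1)^2 + (pre - 1)^2 plus noise, sham change is noise only, and the contrast is active minus sham. The expected contrast is -(s^2 + 0.01) - 2s(m - 1). Average-test power at s = +0.2, noise SD 0.06 / 0.09 / 0.12:

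| m | Expected contrast | Average test |
|---|---|---|
| 0.7 | -0.05 + 0.12 = +0.07 | 99 / 92 / 79% |
| 0.8 | -0.05 + 0.08 = +0.03 | 45 / 31 / 23% |
| 0.9 | -0.05 + 0.04 = -0.01 | 9 / 7 / 7% |
| 1.0 | -0.05 | 85 / 66 / 49% |

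The value m = 0.9 is close to a cancellation point, and at s = +0.1 the mean there is exactly -0.02 + 0.02 = 0. At m = 1.0, an even mix of sub- and super-critical starters, the average test keeps much of its power, because a sizeable shift from near the peak carries most people away from it.

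**5. The missing term in the same model** (moderator reliability 0.7). At s = +0.2 the condition-by-baseline term has about 77-99% power uncorrected across these cases. At s = +0.1 it has about 29-71%. Bonferroni over the 18 outcome lines of Section 9.4.2 (4 effort, 3 E/I, 3 critical dynamics, 4 memory, 4 anti-saccade) gives 93 / 67 / 39% at m = 0.9, s = +0.2. Adding one term for long-range temporal correlations and one for each effort, memory and anti-saccade line makes 18 + 13 = 31 tests, and the middle figure falls to about 60%.

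**The case against.** The strongest reply is that average effects need not be lost. Section 2.1 places the resting brain near the critical point, and in the peaked model with m = 1.0 the average test has about 49-85% power. There the dampening in Section 3 is what one would expect on average, and the planned t-test addresses it. This stands. A reader might infer that mixed regimes always attenuate the average effect, but the documents support neither equal and opposite responses nor any particular mix.

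A second reply concerns behaviour and effort. A reader might infer that those hypotheses are untested too. Section 9.1 ties them to moving closer to criticality, not directly to the resting baseline, and the planned change-with-change correlations partly address that link. Section 9.1 also says brains tend to become more sub-critical during demanding tasks. The relevant regime may therefore be the task regime, and mixing may be less than at rest. This stands, and the point is strong only for long-range temporal correlations.

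Third, the interaction term may itself have low power if shifts are small. That is true. It is a reason to keep the main effect beside it, but not a reason to leave the stated hypothesis without a test.

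**Conclusion.** The point holds in a limited form. For long-range temporal correlations, a primary hypothesis about effect direction has no matching analysis, and this follows from the text without any simulation. For memory-guided saccades, anti-saccades and effort, the dependence on baseline is indirect and partly covered by the planned correlations. Functional E/I and the branching ratio have a fixed predicted direction and are unaffected.

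The loss in the average test cannot be stated as one number. It runs from nearly total (about 5-9% power) to slight, depending on the mix and the response model, both of which are assumed here. When one regime dominates, the average test can do better than the interaction. At m = 0.9 and s = -0.2 it has 100 / 99 / 93%, against 98 / 90 / 74% for the interaction uncorrected.

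Two further inferences would go too far. The power figures in Section 9.2 are not wrong: they reproduce for a single-direction mean effect on motor excitability. Nor does baseline regime bias the crossover comparison: it modifies the effect and is not a rival explanation for it. The matter should be fixed, but it does not invalidate the design.

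**What to change.** 1. In Section 9.4.2, for long-range temporal correlations, prespecify a condition-by-baseline term alongside the main effect. The moderator is pre-stimulation functional E/I minus 1. Keep sham in the model, which guards against regression to the mean, with sex, age and session order as covariates.
2. Count the added terms in the multiplicity correction.
3. Apply the same term to the memory-guided saccade, anti-saccade and effort outcomes as supportive analyses, noting that the moderator is measured at rest.
4. For correlations of E/I change with these outcomes, report change in |E/I - 1| alongside signed change.
5. Reconcile Section 3 (dampening under both protocols; fixed anti-saccade and effort directions) with Sections 6.1.1 and 9.1.
6. State in Section 9.2 that the power figure covers a single-direction mean excitability effect only.

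The cost is protocol wording. Pre-stimulation values are already to be reported under Section 9.4.8, so no new measurement is needed. The downsides are a larger family of tests and modest interaction power if shifts are small (about 29-71% uncorrected at +0.1 under the assumptions above).

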## 9.2 SAMPLE SIZE DETERMINATION

While studies on the effects of continuous theta-burst stimulation (cTBS) and intermittent theta burst stimulation (iTBS) on critical dynamics have never been conducted, power calculations are based on prior work showing that cTBS and iTBS can alter cortical excitability. Effect sizes were taken from a meta-analysis of the effects of cTBS and iTBS on motor cortex excitability, as measured by motor evoked potential via electrodes attached at the contralateral hand (Chung et al. 2016). Two trains of cTBS were found to reliably decrease (Hedge's  $g$  20-30 min after stimulation:  $g = -1.14$ ), and iTBS reliably increase ( $g = .84$ ), motor evoked potentials. Using  $g^*Power$  (Faul et al., 2007), we estimate that if the true effect size remains the same, we will have  $> 95\%$  power to detect a cTBS effect in a sample of 60 participants at  $p < 0.05$ . As such, our target recruitment is set at 60 participants (but will recruit additional participants to reach 60 complete participant-session sets, as needed, due to drop-out). At a later timepoint (50-60 minutes after stimulation) two trains of cTBS have a lasting effect of ( $g = -1.18$ ) while the effects of iTBS are diminished ( $g = -.21$ ). This means that we should still be able to detect a lasting effect of cTBS with  $> 95\%$  power at this later timepoint, while power drops to 36% for iTBS.

While effect sizes can vary in rTMS owing to considerable inter-individual differences in response to stimulation, we are taking additional measures to reduce reliability including participant-specific brain images and neuronavigation, and also the use of two, rather than one train of rTMS.

While this estimate is based on motor cortex excitability alone, this outcome is arguably the most direct measure of the effects of rTMS on cortical excitability. Some caution is warranted because it is unclear whether the effects of cortical excitability on motor cortex are predictive of rTMS effects outside of motor cortex.

